#### 6.1.2 Ancillary treatments

Patients should not receive pre-medication to prevent infusion reaction before the first infusion of PDR001, in order to determine if pre-medication is necessary. If a patient experiences an infusion reaction, he/she may receive pre-medication on subsequent dosing days. The pre-

medication should be chosen per institutional standard of care, at the discretion of the treating physician.

Acute allergic reactions should be treated as needed per institutional standard of care. In the event of anaphylactic/anaphylactoid reactions, this includes any therapy necessary to restore normal cardiopulmonary status. If a patient experiences a severe anaphylactic/anaphylactoid reaction, the infusion should be discontinued immediately. The patient may only resume study treatment following discussion with Novartis.

Patients should be treated in a facility equipped for cardiopulmonary resuscitation. Appropriate resuscitation equipment should be available at the bedside and a physician readily available.

Guidelines on management of PDR001 infusion reactions are provided in [Section 6.3.2](#), [Table 6-4](#).

The CTCAE category of “Infusion related reaction” should be used to describe PDR001 infusion reactions, unless the investigator considers another category, such as “Allergic reaction,” “Anaphylaxis,” or “Cytokine release syndrome” more appropriate in a specific situation.

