### 6.3.2 Follow-up for toxicities

Patients whose treatment is interrupted or permanently discontinued due to an AE or clinically significant laboratory value, must be followed-up at least once a week (or more frequently if required by institutional practices, or if clinically indicated) for 4 weeks, and subsequently at approximately 4-week intervals, until resolution or stabilization of the event, whichever comes first. Appropriate clinical experts should be consulted as deemed necessary. In case of a suspected autoimmune disease AE, the relevant immunological assessments (e.g. rheumatoid factor, anti-DNA Ab, etc.) should be performed. In case of a toxicity suspected to be a cytokine release syndrome, the assessments outlined in [Section 7.2.2.5.6](#) must be performed. All patients

must be followed up for AEs and SAEs for 150 days following the last dose of PDR001. [Table 6-4](#) outlines the follow-up evaluation recommended for selected toxicities.

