**Table 6-4 Follow-up evaluations for selected toxicities**

TOXICITY	FOLLOW-UP EVALUATION AND TREATMENT RECOMMENDATIONS
Infusion Reaction or hypersensitivity reaction	
Grade 1	Decrease infusion rate until recovery of the symptoms.
Grade 2	Stop infusion immediately, and keep line open. Follow institutional guidelines for the management and follow-up of infusion reaction. Restart infusion at 50% of previous rate under continuous observation. Ensure that there is a minimum observation period of 1 hour prior to restarting the infusion.
Grades 3 and 4	If the AE recurs at the reinitiated slow rate of infusion, and despite oral pre-medication, then permanently discontinue study treatment. Discontinue infusion immediately, and discontinue study treatment. Provide supplemental oxygen, fluids, and other resuscitative measures as needed. Monitor vital signs (e.g., blood pressure, pulse, respiration, and temperature) every 15 ± 5 minutes until resolution.
Cytokine Release Syndrome (CRS)	
Grade 2	See instructions for Grade 2 Infusion Reaction above.
Grade 3 or Grade 4	Discontinue study treatment. Follow-up CRS as per institutional guidelines. Take blood for cytokine measurements as specified in Section 7.2.2.5 Laboratory evaluations
Ocular (uveitis, eye pain, blurred vision)	
Grade 1	Continue study treatment without dose modification. Ophthalmology consultation.
Grade 2	Hold study treatment. Urgent ophthalmology consultation. Upon resolution to ≤ Grade 1 may consider resuming study treatment without dose reduction after discussion with the Novartis Medical Monitor and in consultation with ophthalmology.
Grade 3 or Grade 4	Discontinue study treatment. Urgent ophthalmology consultation.
Pulmonary (Pneumonitis)	
Grade 1	Consider study treatment hold. Manage per institutional practice. Consider resuming study treatment upon radiographic evidence of improvement.
Grade 2	Hold study treatment. Pulmonary and infection workup. Upon resolution to ≤ Grade 1, may resume study treatment without dose modification.
Grades 3 and 4	Discontinue study treatment.
Cardiovascular	
ECG QTc-Interval prolonged; hypertension	
Grade 3	Hold study treatment. Upon resolution to Grade ≤ 1 or baseline (hypertension, QTc) or < 30 msec difference from baseline (QTc) within ≤ 7 days, may resume study treatment without dose modification after discussion with the Novartis Medical Monitor. Baseline ECG refers to ECG(s) collected at screening.

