Grade 3 or Grade 4, not associated with symptoms or clinical manifestations of pancreatitis***	Continue study treatment. If levels do not resolve to ≤ Grade 2 within ≤ 14 days after the initial report, hold study treatment. Upon resolution to ≤ Grade 2, may resume study treatment without dose modification, after discussion with the Novartis Medical Monitor.
Pancreatitis	
Grade 2/radiologic evidence	Hold study treatment. Manage per institutional practice. Upon resolution to ≤ Grade 1, may resume study treatment without dose modification, if no clinical evidence of pancreatitis and after discussion with the Novartis Medical Monitor.
Grades 3 or Grade 4	Discontinue study treatment.
Renal	
Serum creatinine	
Grade 2	Hold study treatment. Manage per institutional practice. Upon resolution to ≤ Grade 1, may resume study treatment without dose modification after discussion with the Novartis Medical Monitor.
Grade 3 or 4	Discontinue study treatment.
Musculoskeletal	
Grade 2 or Grade 3	Hold study treatment. Consider resuming study treatment without dose modification upon resolution to ≤ Grade 1 with appropriate management.
Grade 4	Discontinue study treatment. In some cases, resuming study treatment may be considered after discussion with the Novartis Medical Monitor and consultation with a rheumatologist.
Endocrine	
Hypothyroidism or hyperthyroidism	
Grade 2	May continue study treatment without dose modification. Management according to institutional practice.
Grade 3	Hold study treatment. Upon resolution to Grade ≤ 1 with appropriate management, may resume study treatment without dose modification.
Grade 4	May resume therapy following resolution or control with physiologic hormone replacement.
Other endocrine disorders	
Grade 2 and Grade 3	Hold study treatment. Upon resolution to Grade ≤ 1 with appropriate management, may resume study treatment without dose modification.
Grade 4	Hold study treatment. Grade 4 treatment-related endocrinopathies, such as adrenal insufficiency, adrenocorticotrophic hormone (ACTH) deficiency, hyper- or hypothyroidism, or glucose intolerance, which resolve or are adequately controlled with physiologic hormone replacement (corticosteroids, thyroid hormones) or glucose-controlling agents, respectively, may not require discontinuation after discussion with and approval from the Novartis Medical Monitor.
Neurology	

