Grade 1	Consider study treatment hold, particularly for clinical suspicion of Guillain-Barre syndrome, encephalitis, aseptic meningitis, transverse myelitis, or peripheral neuropathy.
Grade 2	Hold study treatment. In some cases, resuming study treatment may be considered after discussion with the Novartis Medical Monitor.

TOXICITY	FOLLOW-UP EVALUATION AND TREATMENT RECOMMENDATIONS
Grade 3 or Grade 4	Discontinue study treatment.
Dermatology (rash) Grade 1 Grade 2 Grade 3 or Grade 4 Bullous dermatitis Stevens-Johnson syndrome (SJS), or Lyell syndrome/toxic epidermal necrolysis (TEN)	Continue study treatment without dose modification. Topical steroids, antihistamines, topical emollients. Consider holding study treatment. Topical or oral steroids, antihistamines. If study treatment is held and resolution to $\leq$ Grade 1, resume study treatment without dose modification. Hold study treatment. Manage per institutional practice. After resolution to $\leq$ Grade 1, consider resuming study treatment after discussion with the Novartis Medical Monitor. Hold study treatment. Grade 1-2 bullous dermatitis: discussion with the Novartis Medical Monitor is required before considering resuming study treatment. Grade 3 bullous dermatitis: consider resuming therapy after expert consultation and documented discussion with the Novartis medical monitor. Grade 4 bullous dermatitis: discontinue study treatment. Permanently discontinue study treatment.

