The occurrence of adverse events should be sought by non-directive questioning of the patient (subject) during the screening process after signing informed consent and at each visit during the study. Adverse events also may be detected when they are volunteered by the patient (subject) during the screening process or between visits, or through physical examination, laboratory test, or other assessments. As far as possible, each adverse event should be evaluated to determine:

1. The severity grade (CTCAE Grade 1-4)
2. Its duration (Start and end dates)

3. Its relationship to the study treatment (Reasonable possibility that AE is related: No, Yes)
4. Action taken with respect to study or investigational treatment (none, dose adjusted, temporarily interrupted, permanently discontinued, unknown, not applicable)
5. Whether medication or therapy was given (no concomitant medication/non-drug therapy, concomitant medication/non-drug therapy)
6. Outcome (not recovered/not resolved, recovered/resolved, recovering/resolving, recovered/resolved with sequelae, fatal, unknown)
7. Whether it is serious, where a serious adverse event (SAE) is defined as in [Section 8.2.1](#) and which seriousness criteria have been met

All adverse events should be treated appropriately. If a concomitant medication or non-drug therapy is given, this action should be recorded on the Adverse Event CRF.

Once an adverse event is detected, it should be followed until its resolution or until it is judged to be permanent, and assessment should be made at each visit (or more frequently, if necessary) of any changes in severity, the suspected relationship to the study treatment, the interventions required to treat it, and the outcome.

Progression of malignancy (including fatal outcomes), if documented by use of appropriate method (for example, as per irRC or as per RECIST), should not be reported as a serious adverse event.

Adverse events separate from the progression of malignancy (example, deep vein thrombosis at the time of progression or hemoptysis concurrent with finding of disease progression) will be reported as per usual guidelines used for such events with proper attribution regarding relatedness to the drug.

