## **8.1.2 Laboratory test abnormalities**

### **8.1.2.1 Definitions and reporting**

Laboratory abnormalities that constitute an Adverse event in their own right (are considered clinically significant, induce clinical signs or symptoms, require concomitant therapy or require changes in study treatment), should be recorded on the Adverse Events CRF. Whenever possible, a diagnosis, rather than a symptom should be provided (e.g. anemia instead of low hemoglobin). Laboratory abnormalities that meet the criteria for Adverse Events should be followed until they have returned to normal or an adequate explanation of the abnormality is found. When an abnormal laboratory or test result corresponds to a sign/symptom of an already reported adverse event, it is not necessary to separately record the lab/test result as an additional event.

Laboratory abnormalities, that do not meet the definition of an adverse event, should not be reported as adverse events. A Grade 3 or 4 event (severe) as per CTCAE does not automatically indicate a SAE unless it meets the definition of serious as defined below and/or as per investigator's discretion. A dose hold or medication for the lab abnormality may be required by the protocol in which case the lab abnormality would still, by definition, be an adverse event and must be reported as such.

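### Section 6.1.2 leaves resumption open after a severe anaphylactic reaction, while the Table 6-4 row it cites discontinues study treatment at Grades 3 and 4 with no resumption option

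*Protocol*

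**What the plan says.** Protocol Section 6.1.2 (Ancillary treatments) deals with a severe anaphylactic or anaphylactoid reaction in two steps. The infusion is stopped at once. Then: "The patient may only resume study treatment following discussion with Novartis". No CTCAE grade is given. The section goes on to name Section 6.3.2, Table 6-4, as the place for guidance on infusion reactions.

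Table 6-4 has a row for infusion or hypersensitivity reactions. At Grades 3 and 4 it says: "Discontinue infusion immediately, and discontinue study treatment". Supportive measures and vital-sign monitoring follow, with nothing about restarting. At Grade 2 the infusion is stopped, the patient is observed for at least an hour, and the infusion restarts at half the previous rate; no sponsor discussion is required. The row also contains this instruction: "If the AE recurs at the reinitiated slow rate of infusion, and despite oral pre-medication, then permanently discontinue study treatment". The extracted table prints that sentence beside the Grades 3 and 4 label, but it presupposes a restart at a slower rate and so belongs by content to Grade 2.

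**The concern.** An investigator whose patient has had a Grade 3 or 4 anaphylactic reaction would get different answers from the two places. Section 6.1.2 says treatment can restart once the sponsor has been consulted. Table 6-4 says treatment ends. At stake is whether a patient may be re-exposed after a potentially life-threatening reaction. There is also a smaller reporting consequence: SAP Section 3.1.6 tabulates patients who were not discontinued after meeting withdrawal criteria, and whether a rechallenged patient belongs in that count depends on which text governs.

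**Working it through.** No arithmetic applies. The check is whether the two texts reach the same patient, and whether the table row is final.

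**1. Same event.** Anaphylaxis is a hypersensitivity reaction, so the Table 6-4 row covers it. Section 6.1.2 itself lists anaphylaxis among the terms that may be used to report an infusion reaction.

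**2. Same grade.** Section 6.1.2 says only severe. Two other places link that word to a grade:
- Section 8.1.2.1, on laboratory abnormalities, has "A Grade 3 or 4 event (severe) as per CTCAE".
- Section 8.1.1 maps severe to Grade 3 and life-threatening to Grade 4, but only for events that CTCAE does not grade.

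Neither was written for anaphylaxis. Both point the same way, and nothing in the protocol offers another meaning. On either mapping the two instructions overlap at Grade 3 at least.

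**3. Is the row final?**

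| Evidence for final | Where |
|---|---|
| Study treatment discontinuation is defined as permanent | Glossary |
| Only two states are named: "Patients whose treatment is interrupted or permanently discontinued due to an AE or clinically significant laboratory value" | Section 6.3.2 |
| The action codes for adverse events separate the two and offer no reversible discontinuation: "dose adjusted, temporarily interrupted, permanently discontinued" | Section 8.1.1 |
| Temporary stops are worded as a hold | Table 6-4 throughout |
| Where a return after discontinuation is intended, the row says so: "In some cases, resuming study treatment may be considered after discussion with the Novartis Medical Monitor and consultation with a rheumatologist" | Table 6-4, musculoskeletal, Grade 4 |
| Dose modifications are to follow Sections 6.3.1 and 6.3.2 | Section 6.1.1 |

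The row also treats stopping the infusion and stopping study treatment as two separate actions and requires both; Section 6.1.2 requires only the first. If the row were not final, a first Grade 3 or 4 reaction would be handled more leniently than a Grade 2 reaction that recurs on slow re-infusion, which ends treatment permanently.

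**4. Does 6.1.2 present itself as an exception?** No. It never says that it overrides the table; it refers to the table for guidance.

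**The case against.** The case for leaving the text alone has real content.

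- **The table is advisory in tone.** Section 6.3.2 calls its evaluations recommended, and 6.1.2 calls them guidelines. This stands, but Section 6.1.1 still directs that dose modifications follow it.
- **The row lacks the word *permanently*.** The SJS/TEN row has it: "Permanently discontinue study treatment". The musculoskeletal row pairs plain discontinuation with a possible return. So the plain wording does not by itself rule out resumption. This weakens the final reading, although in the musculoskeletal row the exception is written in, and in the infusion-reaction row it is not.
- **Sponsor-discussion exceptions exist elsewhere.** Sections 6.1.3 and 6.3.1 require discontinuation after more than two consecutive skipped doses and then allow continuation after discussion with the sponsor. Section 6.3.1 also allows resumption after a DLT following documented discussion, which in Phase I could include a Grade 3 or 4 infusion reaction. The skipped-dose exceptions are stated beside the rule they modify. The DLT clause does not name infusion reactions and would not settle Phase II.
- **Section 7.1.4 lists adverse events among reasons for which treatment may, rather than must, be discontinued.** That is a general list of reasons, not a rule for this reaction.

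A reader might also infer more than the texts support. Table 6-4 uses the phrase for discontinuing study treatment 22 times, 2 of them with *permanently*, and one could argue that if 6.1.2 is right the other 22 - 2 = 20 instructions become reversible, including those for pneumonitis and myocarditis. That does not follow: the sentence in 6.1.2 is limited to anaphylactic reactions and can be read as specific to them. Nor does the protocol define severe as Grade 3 or 4 for this event.

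**Conclusion.** The inconsistency is real and should be corrected. Section 6.1.2 permits a sponsor-gated restart; the table row it cites ends treatment and offers none. The balance of the protocol's own usage favours reading the row as final. The conclusion rests on two assumptions: that severe covers at least Grade 3, and that discontinuation carries its glossary meaning in this row.

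The size is modest. No anaphylaxis case is reported, so no count of affected patients can be given. Enrolment closed on 22-Mar-2018, and 25 patients were still on treatment on 06-May-2019; the documents give no later figure. A reader might infer that sites may rechallenge on their own authority or that results are compromised. Neither is supported: Section 6.1.2 makes sponsor discussion a condition of restarting, and no efficacy analysis is affected. This is a wording conflict in a safety instruction.

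**What to change.** Replace the resumption sentence in Section 6.1.2 with:

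> For Grade 3 or 4 anaphylactic/anaphylactoid reactions, permanently discontinue study treatment (see Table 6-4); manage lower-grade reactions per Table 6-4.

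Add *permanently* to the Grades 3 and 4 entry of the infusion or hypersensitivity row in Table 6-4. Do not attach a sponsor-discussion step to lower grades, because the Grade 2 rule lets the infusion restart without one and a new conflict would result.

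The cost is one sentence, one word, a short written amendment with IRB/IEC approval under Section 12.1, and a note to sites still treating patients. The downside is that the sponsor-gated rechallenge option disappears. If the sponsor wants to keep that option, it should be written into the Table 6-4 row, as was done for Grade 4 musculoskeletal events. Aligning to the stricter row is preferred here because that row is the sponsor's own instruction for the graded event.

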### **6.1.3 Treatment duration**

A patient may continue treatment with PDR001 until the patient experiences unacceptable toxicity, confirmed disease progression per irRC and/or treatment is discontinued at the discretion of the investigator or the patient. Patients will not be withdrawn from the study due to progressive disease per RECIST. Refer to [Section 7.1.4](#) and [Section 7.1.6](#).

If more than 2 consecutive doses of PDR001 have to be skipped due to PDR001-related toxicities, then the drug should be permanently discontinued. If a patient who misses more than 2 consecutive doses due to a PDR001-related toxicity is experiencing clinical benefit, and in the opinion of the investigator it is in the patient’s best interest to remain on study, then the patient may continue treatment after discussion with Novartis.

## **6.2 Dose escalation guidelines**

### **6.2.1 Starting dose rationale**

PDR001 cross reacts with monkey PD-1 but not rodent PD-1; therefore, the starting dose selected for this study is based on 4-week GLP toxicology studies performed in cynomolgus monkeys. PDR001 is a naked monoclonal antibody that does not have agonist activity, and will be administered to patients with advanced malignancies; therefore the starting dose is based on the ICH S9 guidance. The HNSTD was 100 mg/kg, administered i.v., once weekly. As PDR001 will be administered i.v. and it is generally accepted that antibody therapeutics allometrically scale according to body weight, the human equivalent dose (HED) of the HNSTD is 100 mg/kg. The maximum permitted starting dose in patients is  $1/6 \times 100$  mg/kg, or 17 mg/kg administered weekly. Based on the prior clinical experience with nivolumab and pembrolizumab ([Topalian 2012](#), [Topalian 2014](#), [Hamid 2013b](#), [Robert 2014](#)), and with the reasonable assumption that PDR001 will have similar PK/PD properties as those comparators, PDR001 is expected to demonstrate antitumor activity at doses of 2-3 mg/kg dosed every 2-3 weeks. In order to evaluate the safety, PK and antitumor activity of PDR001 across a range of doses, the

recommended starting dose in this study will be 1 mg/kg, i.v., every 2 weeks, which is well below the maximum permitted starting dose.

## 6.2.2 Provisional dose levels

Table 6-2 describes the starting dose and the dose levels that may be evaluated during this trial.

**Table 6-2 Provisional dose levels**

Dose level	Proposed dose*	Increment from previous dose
-1**	0.3 mg/kg	-70%
1**	1 mg/kg	Starting dose
2	3 mg/kg	300%
3	10 mg/kg	333%

\*It is possible for additional and/or intermediate dose levels to be added during the course of the study Cohorts may be added at any dose level below the MTD in order to better understand safety, PK or PD. Multiple dose levels below the MTD may be evaluated simultaneously in order to obtain PK and PD data across a range of doses and to establish the RP2D.

\*\*Dose level -1 represents a treatment dose for patients requiring a dose reduction from the starting dose level. No dose reduction below dose level -1 is permitted for this study.

## 6.2.3 Guidelines for dose escalation and determination of MTD or RP2D

For the purposes of dose escalation decisions, each cohort will consist of 3 to 6 newly enrolled patients who will be treated at the specified dose level. The first cohort will be treated with the starting dose of 1 mg/kg.

Patients must complete a minimum of 1 cycle of treatment with the minimum safety evaluation and drug exposure or have had a DLT within the first cycle of treatment to be considered evaluable for dose escalation decisions (Section 10.1.4). Also, for the dose-exposure analysis, patients must have received at least one dose of PDR001 during Cycle 1 and have sufficient PK samples in cycle 3 to evaluate the  $AUC_{(0-336h)}$  (Section 10.1.5). Dose escalation decisions will occur when the cohort of patients has met these criteria. If only 2 patients in a cohort are evaluable and neither patient has experienced a treatment-related toxicity > CTCAE grade 1, dose escalation decisions may be considered.

Dose escalation decisions will be made by Investigators and Novartis study personnel. Decisions will be based on a synthesis of all relevant data available from all dose levels evaluated in the ongoing study including safety information, DLTs, all CTCAE Grade  $\geq 2$  toxicity data during Cycle 1, and available PK, including Bayesian dose-exposure modeling, and PD data from evaluable patients. The recommended dose for the next cohort of patients will be guided by the Bayesian linear model and the BLRM with EWOC principle evaluating the probability of DLT (Section 10.4.2).

